5.6. Potential Benefits

Based upon literature review and pre-clinical evaluations performed to date, it is expected that the baroloop system may provide benefit to the subject by reducing blood pressure to or toward recommended target blood pressure values as outlined in the 2018 ESC/ESH Guidelines for the management of arterial hypertension. Without the baroloop system, blood pressure may remain poorly controlled in this population. The potential benefits include a reduction in blood pressure toward more normal values, which has been associated with a reduction in cardiovascular risks associated with hypertension (the 2018 ESC/ESH Guidelines for the management of arterial hypertension).

However, the actual benefits are not known and are the subject of this investigational study. There may be no direct benefits of study participation. Nevertheless, subject participants will undergo an enhanced level of clinical scrutiny of health compared to routine clinical care, which may provide some indirect health benefits.

6. Statistical Analysis Plan

6.1. Overview

The primary objective of this study is to characterize the safety and feasibility of the baroloop System in subjects with uncontrolled or resistant hypertension. All subjects will be followed on an intent-to-treat basis (ITT). The device performance will also be assessed based on a per-protocol analysis of the primary safety and feasibility endpoints and secondary efficacy endpoints. An intent-to-treat analysis, along with other secondary analyses, will also be completed and reported.

This is not a hypothesis driven study, and no formal power analysis or hypothesis-driven statistical analysis has or will be performed. Standard summary statistics will be calculated for all study variables. For continuous variables, statistics will include means, standard deviations, medians and ranges. Categorical variables will be summarized using frequency distributions.

The primary endpoints will be analyzed on an intent-to-treat (ITT) basis, for which data from all subjects enrolled will be included. In order to evaluate a true treatment effect, the primary analysis will include those subjects achieving technical success, the definition of which includes successful completion of the study procedure.

If there are no more than 4 failures to implant, combined with a safety level that is determined by the independent DSMB to be acceptable, together with any reduction in blood pressure as a result of the baroloop therapy, this will be considered a successful outcome to this First-in-Human study.

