6.3. Primary Feasibility Endpoint

The primary feasibility endpoint is technical success, defined as the ability of the baroloop System to be placed around a vagal nerve and the ability to stimulate at 14 days post-implantation.

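### Section 6.1 names two different primary analysis sets, one of them selected on the primary feasibility endpoint itself, and adds a per-protocol analysis with no defined set

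*Combined protocol and SAP*

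**What the plan says.** Section 6.1 makes three statements about who is analysed.

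- For the primary endpoints: "The primary endpoints will be analyzed on an intent-to-treat (ITT) basis, for which data from all subjects enrolled will be included".
- In the very next sentence: "In order to evaluate a true treatment effect, the primary analysis will include those subjects achieving technical success". The sentence ends by noting that technical success includes completing the procedure successfully.
- In its opening paragraph: "The device performance will also be assessed based on a per-protocol analysis of the primary safety and feasibility endpoints and secondary efficacy endpoints", followed by "An intent-to-treat analysis, along with other secondary analyses, will also be completed and reported".

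Section 6.3 then states: "The primary feasibility endpoint is technical success, defined as the ability of the baroloop System to be placed around a vagal nerve", together with "the ability to stimulate at 14 days post-implantation". The synopsis and Section 4.2.2 put the same endpoint at Day 14/21.

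Under Section 4.11 a subject is enrolled at skin incision for the implant. Only people excluded before that moment are kept out of the primary analysis.

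**The concern.** The two adjacent sentences in 6.1 cannot both describe the primary analysis. A subject whose implant fails is enrolled, so belongs to the first set, but is not a technical success, so is absent from the second. Nothing in the plan ranks the sets or assigns one to each endpoint. The opening paragraph adds to the doubt by listing intention to treat alongside secondary analyses. The per-protocol set has no membership rule in Section 6, in 9.16 on deviations, or in the Section 12 definitions.

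The second sentence also selects on an outcome. Technical success is the primary feasibility endpoint, so an analysis limited to technical successes cannot show a feasibility failure. It also omits from the primary major adverse event (MAE) rate any event in a subject who had surgery but did not reach technical success, although device- or procedure-related serious events are part of that composite.

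At stake is which figure is the headline for each primary endpoint, and whether that choice could be made after the data are seen. The synopsis and Section 4.1 plan comparisons with historical results for other devices, and these need a known denominator.

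**Working it through.** **No figure to reproduce.** The plan gives no sample-size or rate calculation: "This is not a hypothesis driven study, and no formal power analysis or hypothesis-driven statistical analysis has or will be performed". The check is a reading of the text plus an illustration.

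**Inputs.** Maximum enrolled: 10 (Section 4.4). The number of technical failures *f* and the number of subjects with an MAE *m* are assumptions, shown over a range.

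**Feasibility.** All enrolled: (10 − *f*)/10. Technical-success set: (10 − *f*)/(10 − *f*), which is always 1. Intervals are exact Clopper-Pearson 95%. They are an addition, since Section 6.5 specifies number and percent for categorical variables.

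| *f* | All enrolled | 95% CI | Technical-success set |
|---|---|---|---|
| 0 | 10/10 = 100% | 69.2–100% | 10/10 = 100% |
| 1 | 9/10 = 90% | 55.5–99.7% | 9/9 = 100% |
| 2 | 8/10 = 80% | 44.4–97.5% | 8/8 = 100% |
| 3 | 7/10 = 70% | 34.8–93.3% | 7/7 = 100% |
| 4 | 6/10 = 60% | 26.2–87.8% | 6/6 = 100% |

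No interval is given for the last column because that figure is fixed by the selection and not estimated.

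**MAE rate.** All enrolled: *m*/10. In the technical-success set the rate runs from max(0, *m* − *f*)/(10 − *f*), with as many events as possible among the failures, to min(*m*, 10 − *f*)/(10 − *f*), with as many as possible among the successes.

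| *m* | All enrolled | *f* | Technical-success set |
|---|---|---|---|
| 1 | 1/10 = 10% | 1 | 0/9 = 0% or 1/9 = 11.1% |
| 1 | 1/10 = 10% | 4 | 0/6 = 0% or 1/6 = 16.7% |
| 3 | 3/10 = 30% | 1 | 2/9 = 22.2% or 3/9 = 33.3% |
| 3 | 3/10 = 30% | 2 | 1/8 = 12.5% to 3/8 = 37.5% |
| 3 | 3/10 = 30% | 4 | 0/6 = 0% to 3/6 = 50% |

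The rate can move either way, so this shows ambiguity and not a bias in one direction.

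**Range of *f*.** Four is not an upper bound. The limit of 4 in Sections 6.1 and 9.13 counts failures to implant, while technical failure under 6.3 also covers a device that is in place but cannot stimulate.

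**Time point.** Section 6.3 and the Section 12 entry for procedural success use 14 days; the synopsis and 4.2.2 use Day 14/21. The first note in Section 4.23 lets the first titration be postponed to day 21 at the latest, which appears to explain the difference. The endpoint is ability to stimulate, so a postponed titration is not in itself a failure.

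**The case against.** The best defence is the purpose clause. The sentence on technical success is about a treatment effect, and neither primary endpoint is one: blood pressure is, and it is secondary (Section 6.4). The only sentence that names the primary endpoints puts them in all enrolled. Section 4.11 agrees, and the stopping rule in 9.13 and the success criterion both need failed implants to be counted: "If there are no more than 4 failures to implant, combined with a safety level that is determined by the independent DSMB to be acceptable". This probably is the intent. But the sentence refers to the primary analysis without restriction, and a reader should not have to infer its scope.

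A second argument is that technical success in 6.1 might mean only that the procedure was completed. An implanted subject who could not be stimulated would then be in the set and fail the endpoint, so feasibility would not be exactly 100%. The shared term makes this the less likely reading, the added clause is compatible with 6.3, and failed procedures would still be left out.

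A third is that little depends on it. Section 4.14 keeps all enrolled subjects in safety follow-up, Section 7 has serious events adjudicated and included, intention to treat is reported in any case, and the Data Safety Management Board judges safety without a numeric MAE threshold. All of this stands and limits the consequence. It does not say which figure leads the report.

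**Conclusion.** The concern holds. As written, 6.1 gives incompatible primary sets, and the second one, read with 6.3, makes the feasibility result uninformative and can leave MAEs out of the primary safety rate. With 10 enrolled and 4 technical failures, feasibility is 60% or 100% depending on the sentence followed; with 3 subjects having an MAE, the safety rate is 30% or between 0% and 50%. These counts are assumed. With no technical failures the sets coincide and nothing changes. The 100% figure rests on technical success meaning the same in 6.1 and 6.3.

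No type I error or power is affected. It should be fixed before analysis, but it does not threaten the conduct of the study. The differing time point is a minor companion issue.

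**What to change.** Replace the two conflicting sentences in 6.1 with wording such as:

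> Technical success and the 6-month MAE rate are analysed in all enrolled subjects (enrolled at skin incision), as the single primary set and denominator. Subjects achieving technical success form a supportive set, used mainly for blood pressure outcomes.

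Then:

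- Define the per-protocol set and label it supportive, or merge it with the technical-success set.
- Stop listing intention to treat among the secondary analyses.
- State one time point for the feasibility endpoint in 6.3, the synopsis and 4.2.2, in light of 4.23. Align the Section 12 procedural success entry and the feasibility wording in 4.1 with it.
- Since 6.6 rules out imputation and uses available data only, state how a subject who leaves before six months without an MAE counts in the denominator.

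This changes wording only and needs no new data. Section 10.3 may require Ethics Committee and Competent Authority approval. The drawback for the sponsor is that the feasibility figure, and possibly the MAE figure, may look less favourable.

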Figure 1: Schematic of the elementary parameterization of a stimulation pulse	22
Figure 2: baroloop Trial Screening and Enrollment Scheme	38

 neuroloop	Confidential	Protocol – The baroloop Study
--	---------------------	-------------------------------------

1. Protocol Synopsis

Sponsor	neuroloop GmbH [name] [name] Germany [contact] Email: [contact] Website: www.neuroloop.de
Principal Investigators	
Netherlands:
 [name] Division Internal Medicine and Dermatology Dept. of Vascular Medicine UMC Utrecht [name] [name]
	
Germany:
 Univ. [name]. med. [name] Experimentelle Gefäßmedizin und Transplantationsforschung Klinik für Nieren- und Hochdruckerkrankungen Medizinische Hochschule Hannover [name] [name]
Sponsor Representative	MAXIS Medical GmbH
	[name]
	[name]
	Germany
	[contact]
	[contact]
	Email: [contact]
Medical Monitor	[name].
	Chief Medical Officer
	MAXIS Medical GmbH
Protocol Title	A First in Human Study of Safety and Feasibility of baroloop
Short Title	The baroloop Study
Protocol number	Protocol Number: BL_CIP-FIH
	Revision: 2.4
	Date: 03 March 2021
Device	baroloop System
Indication for Use	The baroloop System is intended to be used to treat hypertension.

Objectives	
The primary objectives are to assess the safety and feasibility of the baroloop device for the treatment of subjects with hypertension (HTN).
 
The secondary objective is to document the effect of the baroloop device on the blood pressure and quality of life in subjects with hypertension (HTN).

Study Design	Non-randomized, prospective, single-arm, multi-center feasibility trial for subjects with hypertension
Number of Subjects	Up to ten (10) subjects
Number of Sites	Up to three (3) centers in Europe
Primary Safety Endpoint	
Composite Major Adverse Event (MAE) Rate at six (6) month post-treatment including:
 
• All causes of death• Hospitalization for hypertensive crisis post-titration• Any device or procedure-related serious adverse event 
All MAEs to be adjudicated by an independent Data Safety Management Board (DSMB).

Primary Feasibility Endpoint	The ability of the baroloop System to be placed around a vagal nerve and to stimulate at Day 14/21 post-implantation.

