4.2.2. Feasibility

The ability of the baroloop Systems to be placed around a vagal nerve and the ability to stimulate at Day 14/21 post-implantation.

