--	---------------------	-------------------------------------

Spontaneous MI (>72 h after the index procedure):

Any one of the following criteria:

- Detection of rise and / or fall of cardiac biomarkers (preferably troponin) with at least one value above the 99th percentile URL, together with evidence of myocardial ischemia with at least one of the following:
 - Symptoms of ischemia
 - ECG changes indicative of new ischemia [new ST-T changes or new left bundle branch block [LBBB]
 - New pathological Q waves in at least two contiguous leads
 - Imaging evidence of new loss of viable myocardium or new wall motion abnormality
- Sudden, unexpected cardiac death, involving cardiac arrest, often with symptoms suggestive of myocardial ischemia, and accompanied by presumably new ST elevation, or new LBBB, and / or evidence of fresh thrombus by coronary angiography and / or at autopsy, but death occurring before blood samples could be obtained, or at a time before the appearance of cardiac biomarkers in the blood.
- Pathological findings of an acute myocardial infarction.

Post-Procedure Intensive Care Unit Time

Number of hours a patient is in an intensive care unit prior to discharge or moving to a step down or standard care unit.

Post-Procedure Length of Hospital Stay

Number of days from the end of the procedure until the patient is discharged from the hospital. This does not include time spent in a skilled care facility.

Procedural Success

Successful delivery of the investigational baroloop System placed around a vagal nerve providing effective stimulation at 14 days post-implantation.

Procedure Time

Number of minutes needed to perform the index procedure from time of initial skin incision to time of final skin closure and final intra-operative device testing.

Renal Failure

Need for dialysis or a laboratory finding of serum creatinine > 3.5 mg / dL.

Respiratory Failure

The need for mechanical ventilation beyond the first 24 hours post-index procedure (and / or reintervention) or the need for re-intubation or ventilator support after the first 24 hours (unless the subject was ventilator dependent pre-procedure).

Stroke Diagnostic Criteria:

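### The Section 6.1 success rule leaves its blood pressure limb undefined with a zero threshold, and its implant-failure count has no denominator and misses devices that later cannot stimulate

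*Combined protocol and SAP*

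**What the plan says.** Section 6.1 is the only place that defines a successful outcome. The rule has three limbs. The first begins "If there are no more than 4 failures to implant", the second is a DSMB judgement on safety, and the third reads "together with any reduction in blood pressure as a result of the baroloop therapy, this will be considered a successful outcome". The DSMB limb is not questioned here.

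The same section states that the study is not hypothesis driven. It names three analysis sets. One is intent-to-treat: "The primary endpoints will be analyzed on an intent-to-treat (ITT) basis, for which data from all subjects enrolled will be included". A second is the technical-success set: "the primary analysis will include those subjects achieving technical success". The third is a per-protocol analysis covering the primary endpoints and the secondary efficacy endpoints. None is assigned to the success rule.

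Section 6.4 lists the blood pressure endpoints: the change during intraoperative stimulation, and mean reductions in 24-hour ambulatory and in office pressure, systolic and diastolic, at 1, 3, 6, 12, 18 and 24 months. None is ranked.

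Section 4.4 allows up to 10 subjects with no minimum. Section 9.13 stops the study when implant failures exceed 4, and also allows discontinuation for insufficient recruitment. Section 9.15 requires a final report in any case.

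The primary feasibility endpoint needs placement and stimulation. Its timing varies:

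- Synopsis: "The ability of the baroloop System to be placed around a vagal nerve and to stimulate at Day 14/21 post-implantation"
- Section 4.2.2: "the ability to stimulate at Day 14/21 post-implantation"
- Section 6.3, where it is called technical success: "the ability to stimulate at 14 days post-implantation"
- Section 12, under Procedural Success: "providing effective stimulation at 14 days post-implantation"
- Section 4.1 describes feasibility differently again, as implantation plus the ability to lower blood pressure.

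Section 4.23 lets the first titration take place as late as day 21.

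**The concern.** A success rule should give one answer once the data are in. The blood pressure limb does not: measure, component, visit and analysis set can all be chosen afterwards, and any fall above zero suffices. The limb asks that the fall be caused by the therapy, but no analysis is named to show this in a single-arm study that selects on high blood pressure.

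The failure limb can be counted, but it restates the stopping count in Section 9.13, so every study not stopped on that count satisfies it. It has no denominator, and it does not follow the stimulation half of the primary feasibility endpoint through to day 14 or 21.

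At stake is whether this first-in-human study is labelled a success. Because technical success also defines the primary analysis set, who is analysed is at stake too.

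**Working it through.** The plan gives no power, alpha or sample-size figure, so there is nothing to reproduce. The checks below show how the rule behaves.

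**1. Blood pressure limb.** Section 6.4 gives 2 measures × 2 components × 6 visits = 24 mean changes, plus the intraoperative change. Assume no true effect, no drift and symmetric changes.

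- One named mean change is below zero with probability 0.50 at any n.
- For at least one of k equally correlated normal mean changes, P = 1 − ∫ φ(c) Φ(c√ρ/√(1−ρ))^k dc. The documents give no ρ, so a range is shown.

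| k | ρ = 0.5 | ρ = 0.7 | ρ = 0.9 |
|---|---|---|---|
| 4 (one visit) | 0.80 | 0.73 | 0.63 |
| 24 (all) | 0.96 | 0.89 | 0.74 |

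Entry requires raised office and ambulatory pressures (Section 4.6.1), so regression to the mean would push these figures up. By how much depends on variances that the documents do not give.

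**2. Failure limb, no denominator.** Four failures is 4/10 = 40% of 10 subjects (exact 95% interval 12–74%) and 4/5 = 80% of 5 (28–99%). With 4 or fewer enrolled the limb cannot fail. With X binomial (N, 0.4), P(X ≤ 4) is:

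| N | 10 | 8 | 6 | 5 |
|---|---|---|---|---|
| Limb passes | 0.633 | 0.826 | 0.959 | 0.990 |

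**3. Failure limb, stimulation not counted.** Assume 20% implant failure and N = 10. The implant count passes with P(X ≤ 4 | 10, 0.2) = 0.967, whatever happens to stimulation afterwards. If s is the stimulation-failure rate among implanted subjects, the technical-failure rate is 1 − 0.8 × (1 − s).

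| s | Technical-failure rate | P(at most 4 technical failures) |
|---|---|---|
| 6.5% | 25.2% | 0.920 |
| 20% | 36% | 0.729 |
| 40% | 52% | 0.329 |

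The 6.5% is the hardware-complication rate that Section 2.5.2 cites for epilepsy stimulators, a different lead design. The 20% and 40% are assumptions. Keeping the limit at 4 is for illustration only.

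A case by count: 3 implant failures plus 4 devices that pass testing at surgery but cannot stimulate at the feasibility time point make 7 technical failures in 10. The limb is still met.

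**4. Timing.** Take a subject whose first titration is deferred to between day 14 and day 21, as Section 4.23 permits. Under the synopsis and Section 4.2.2 the assessment can count. Under Section 6.3 the reference point is 14 days, and the subject may be treated as a failure or as not assessed. The same data can therefore give different technical-success sets.

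**The case against.** The strongest reply is that this is a small, descriptive first-in-human study with no hypothesis test, so it needs no formal success criterion. That is right as far as it goes, and nothing here asks for a power calculation or a test. But the sponsor chose to write a success rule, and a rule that is kept must be decidable.

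Read literally, the causal wording excludes an inert device. The protocol also collects relevant evidence: ambulatory monitoring after observed therapy, compliance testing, and Finapres and cuff readings during and after stimulation (Section 4.24). None of this is linked to the rule, and the on/off readings are acute.

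Using the same count for success and for stopping is consistent and not in itself an error. A therapy-caused fall also implies that stimulation worked in at least one subject, but that is not the per-subject count that the endpoint requires.

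A reader might infer more than the documents support:

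- **That the limb could mean every subject, most subjects or any one subject falling.** Section 6.4 words the follow-up endpoints as mean reductions, so such readings match no listed endpoint. What is open is the measure, component, visit and analysis set.
- **That the failure count looks at placement alone.** Failure to implant is undefined, and the implantation procedure (Section 4.22) requires passed impedance tests and a stimulation test. A device that fails at surgery could be counted. Only later inability to stimulate is clearly left out.
- **That no confidence intervals are planned for efficacy.** Section 6.5 mentions 95% intervals in a paragraph on demographic and baseline data, but its heading covers efficacy, so they may already be intended.
- **That a subject first titrated on day 20 plainly fails Section 6.3.** That section asks for ability to stimulate, and such a subject may simply be unassessed at day 14. Section 12 defines a differently named term.

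**Conclusion.** The point holds, and the rule should be corrected. Followed exactly, it can declare success on a blood pressure change chosen after the fact. An inert device would show a fall 50% of the time on one named mean and 74–96% of the time on at least one of 24, assuming no drift and correlations of 0.9–0.5.

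The failure limb becomes nearly automatic as enrolment shrinks: 63% at N = 10 and 99% at N = 5, at a true 40% failure rate. How much omitting later stimulation failure matters is not known. With 20% implant failure at N = 10, the contrast is 97% against 92%, 73% or 33%, depending on a stimulation-failure rate that the documents do not give for this device. A large gap should not be presumed.

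A reader might conclude that the study's results are compromised. They are not: the primary and secondary endpoints are reported regardless, and the DSMB limb still guards safety. The harm is confined to the success label and to who enters the technical-success set.

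**What to change.** **1. Blood pressure limb, one of two options.**

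(a) Remove blood pressure from the success statement, report it descriptively, and align Section 4.1.

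(b) Name one quantity: mean change from baseline to 6 months in 24-hour ambulatory systolic pressure. Six months matches the primary safety time point, and Section 4.34 does not allow drug reduction before then. Choose one of the three analysis sets. Print the 95% confidence interval beside the success statement, and confirm that the intervals in Section 6.5 apply to efficacy data. State that a mean fall alone does not show a device effect, since a zero threshold passes an inert device at least half the time.

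Under either option, state that the change includes regression to the mean and medication changes.

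**2. Failure limb.** In the success rule, count technical failures (placement or stimulation) over the number enrolled, with an exact 95% interval. The sponsor should restate the threshold for that count and for a smaller N, because the present 4 refers to implant failures. Section 9.13 can stay as it is.

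**3. Feasibility wording.** Reconcile the synopsis and Sections 4.1, 4.2.2, 4.23, 6.3 and 12, so that a subject is classified the same way everywhere.

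**Cost.** SAP and protocol wording and two intervals, from data already collected. Success becomes somewhat harder to claim. Under (b), with an assumed SD of change of 8–15 mmHg, a true 5 mmHg fall gives an observed mean fall with probability Φ(5√n/SD): 98–85% at n = 10 and 94–79% at n = 6. The interval half-width, t × SD/√n, is 5.7–10.7 mmHg at n = 10 and 8.4–15.7 mmHg at n = 6, so the result will be imprecise, but visibly so.
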